5.2 Pharmacokinetic Analysis

In general, all PK summary tables will be presented for the PK population.

Individual raw PK concentrations will be displayed with the same precision as received from the bioanalytical laboratory.

Precision for individual PK parameters will be displayed as follows:

- C_{\max} , C_{\min} , CL/F , Vz/F and AUCs will be displayed with the same precision as the raw PK concentration data
- Parameters associated with time (eg, time of maximum concentration [T_{\max}]) will be displayed with 2 decimal places
- Percentages will be displayed with 2 decimal places
- Ratios will be displayed with 2 decimal places
- Coefficient of determination (R^2) and elimination rate constant (λ_z) will be displayed with 4 decimal places

Summary statistics for concentration and PK parameters will be displayed with the same precision as the individual values, with the exception of number of observations (n) and CV% which will be presented with 0 and 1 decimal place, respectively.

5.3 Baseline

Unless otherwise specified, the baseline value will be defined as the last non-missing evaluation prior to the first dose of study drug, including unscheduled assessment(s), if applicable.

5.4 Methods for Handling Missing Data

In general, no imputations of values for missing safety data (ie, blank, “Not Done”, “Not Applicable”, etc.) will be performed and data presentations will reflect the data point as it appears in the Case Report Form (CRF) or electronic data file.

6 STUDY SUBJECTS

Unless otherwise specified, all available data will be listed and summary table for disposition will be presented for all enrolled subjects.

6.1 Disposition

Subject disposition will be summarized by cohort (TMP-301 50 mg BID Fasted, TMP-301 50 mg QD Fasted, TMP-301 XX mg and TMP-301 XX mg), pooled placebo and overall, including:

- Number of subjects screened (if applicable)
- Number of subjects randomized (if applicable)
- Number of subjects who received study drug
- Number (%) of subjects who completed the study
- Number (%) of subjects discontinued from the study overall and by primary reason for discontinuation
- Number (%) of subjects included in each of the analysis populations

The percentages will be calculated using the number of subjects who received study drug.

Listings of subject's disposition, Randomization details, and subjects included in each of the analysis populations will be provided. In addition, a listing of screen failures including reason for failure will be presented.

6.2 Protocol Deviations

All protocol deviations related to study inclusion or exclusion criteria, conduct of the study, subject management, or subject assessment (including PK sample processing deviations) will be listed for the Randomized populations. Information for PK sampling time deviations will be derived programmatically, and presented in a listing.

Deviations will be collected in the clinic deviation tracking system (DTS) and presented in a general protocol deviation listing.

Table 3: Acceptable Windows for Timed PK Blood Specimen Collection Procedures

Elapsed Time	Accepted Window
Pre-dose	No window specified
> 0 hour to \leq 30 minutes	\pm 10 minutes
> 30 minutes to \leq 4 hours	\pm 10 minutes
> 4 hours to \leq 12 hours	\pm 10 minutes
> 12 hours to \leq 24 hours	\pm 10 minutes
> 24 hours to \leq 72 hours	\pm 2 hours
> 72 hours	\pm 4 hours

7 DEMOGRAPHIC AND OTHER BASELINE CHARACTERISTICS

Unless otherwise specified, summary tables for demographics and other baseline characteristics, and all available data will be listed based on the Randomized population.

Demographic and baseline characteristics including age, sex, ethnicity, race, height, weight (at screening), and body mass index (BMI) will be listed and summarized by cohort (TMP-301 50 mg BID Fasted, TMP-301 50 mg QD Fasted, TMP-301 XX mg and TMP-301 XX mg), pooled placebo and overall. Descriptive statistics will be presented for age, height, weight, and BMI, while frequency counts and percentages will be presented for sex, ethnicity, and race.

The following will be presented in listings:

- Medical history
- Prior and concomitant medications
- Alcohol Habits
- Substance Use Habits
- Gynecological History
- Psychiatric History

8 SAFETY ANALYSIS

Unless otherwise specified, summary tables for safety assessments will be presented for the Safety population. All available data will be listed by cohort and subject based on the Randomized population.

8.1 Adverse Events

An AE is defined as any untoward medical occurrence in a clinical investigation subject administered an investigational product and which does not necessarily have a causal relationship with the treatment. An AE can therefore be any unfavorable and unintended sign (including a clinically significant abnormal laboratory finding, for example), symptom, or disease temporally associated with the use of an investigational product, whether or not related to the investigational product.

Treatment-emergent AEs (TEAEs) are AEs not present prior to but reported following the exposure to study treatment or AEs already present that worsen in intensity or frequency following exposure to study treatment.

All TEAEs will be assigned to the last treatment taken by the subject where the date and time of the last treatment dosing is on or before of the start date and time of the event. Any TEAE started during follow-up period will be assigned to the last treatment that the subject has taken.

In case that the time of onset or time of resolution is unknown, treatment-emergent or assignment would be determined considering the worst case scenario and/or on case-by-case basis, as deemed appropriate. Treatment-emergent AEs with missing severity or relationship to study treatment will also be classified to the worst case (eg, severe and/or related, as appropriate) in corresponding summaries.

An overall summary of AEs will be presented by cohort (TMP-301 50 mg BID Fasted, TMP-301 50 mg QD Fasted, TMP-301 XX mg and TMP-301 XX mg), pooled placebo and overall active including:

- Number of AEs reported, overall only
- Number of TEAEs reported
- Number (%) of subjects with at least one TEAE
- Number (%) of subjects with at least one study drug-related TEAEs
- Number (%) of TEAEs by relationship to study treatment (ie, Reasonable Possibility or No Reasonable Possibility)
- Number (%) of TEAEs by severity
- Number of serious AEs (SAEs)
- Number (%) of subjects with at least one SAE
- Number (%) of subjects with at least one study drug-related SAE
- Number (%) of subjects with a TEAE leading to discontinuation
- Number (%) of subjects with outcome of death

Frequency tables will be presented by cohort, pooled placebo and overall:

- Number (%) of subjects with TEAEs by system organ class (SOC) and preferred term

(PT)

- Number (%) of subjects with drug-related TEAEs by SOC and PT
- Number (%) of subjects with TEAEs by relationship to study treatment
- Number (%) of subjects with TEAEs by severity
- Number (%) of subjects with SAEs by system organ class (SOC) and preferred term (PT)

All adverse event data will be presented in a listing.

8.2 Clinical Laboratory Evaluations

General biochemistry, hematology, and urinalysis assessments, and other laboratory tests are listed in Table 3.

Table 4: Clinical Laboratory Assessments

Clinical Laboratory Test Panel	Description
General biochemistry:	Alanine aminotransferase, albumin, alkaline phosphatase, aspartate aminotransferase, bilirubin total and conjugated bilirubin if total bilirubin is elevated, blood urea nitrogen, calcium, chloride, Creatinine phosphokinase (CPK), Bicarbonate (CO ₂), creatinine (including eGFR calculated using the CKD-EPI calculation, cholesterol total, glucose, LDH, phosphorous, potassium, protein total, sodium, triglycerides, and uric acid
Coagulation:	Prothrombin time INR and partial thromboplastin time (aPTT) levels
Endocrinology:	FSH ¹
Hematology:	White cell count with differential (absolute values of neutrophil, lymphocyte, monocyte, eosinophil, and basophil), red cell count, hemoglobin, hematocrit, mean corpuscular volume, and platelet count
Serology ¹	Human immunodeficiency virus (HIV) Ag/Ab Combo, Hepatitis B surface antigen, and Hepatitis C virus
Urinalysis:	Color, clarity, specific gravity, pH, leukocyte, protein, glucose, ketones, bilirubin, blood, nitrite, urobilinogen. Microscopic examination will only be performed if the dipstick test is outside of the reference range for leukocyte, blood, nitrite or protein
Urine drug screen:	Alcohol, amphetamines, barbiturates, benzodiazepines, cannabinoids, cocaine, cotinine, methadone, opiates, phencyclidine, and tricyclic antidepressants
Pregnancy test:	Serum pregnancy test or urine pregnancy test

¹Screening visit only

Laboratory data will be summarized by the type of laboratory test, visit. Descriptive statistics (n, mean, SD, minimum, median, and maximum), and the number of subjects with laboratory test results below, within, and above normal ranges will be tabulated by laboratory test and visit.

All laboratory data will be listed by laboratory panel and test. Laboratory abnormalities and clinically significant abnormalities will also be listed.

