4.1. Inclusion Criteria

1. Provision of signed and dated informed consent form (ICF)
2. Stated willingness to comply with all study procedures and availability for the duration of the study
3. Healthy adult male or female
4. If male, meets one of the following criteria:
 - a. Is able to procreate and agrees to use one of the accepted contraceptive regimens and not to donate sperm from the first study drug administration to at least 90 days after the follow-up visit. An acceptable method of contraception includes one of the following:
 - Abstinence from heterosexual intercourse
 - Male condom with spermicide or male condom with a vaginal spermicide (gel, foam, or suppository)

Or

- b. Is unable to procreate; defined as surgically sterile (ie, has undergone a vasectomy at least 180 days prior to the first study drug administration)
5. If female, meets one of the following criteria:
 - a. Physiological postmenopausal status, defined as the following:
 - absence of menses for at least 12 months prior to the first study drug administration (without an alternative medical condition); and
 - Follicle stimulating hormone (FSH) levels ≥ 40 mIU/mL at Screening;
6. Aged at least 18 years but not older than 59 years, inclusive, at the time of informed consent
7. Body mass index (BMI) within 18.5 kg/m^2 to 32.0 kg/m^2 , inclusively
8. Minimum body weight of at least 50.0 kg

9. Non- or ex-smoker (*An ex-smoker is defined as someone who completely stopped using nicotine products for at least 90 days prior to the first study drug administration*)
10. Must be willing to abstain from drinking coffee or caffeine containing beverages during the study, except where part of the study procedures
11. Has supine blood pressure and pulse rate within the following ranges after 5 minutes rest: systolic blood pressure 90 to 140 mmHg, diastolic blood pressure 50 to 90 mmHg, and pulse rate 45 to 90 bpm at Screening and at check in
12. Have no clinically significant diseases captured in the medical history or evidence of clinically significant findings on the physical examination (including vital signs) and/or ECG, as determined by an Investigator
13. Has clinical laboratory test results within the reference ranges of the testing laboratory, with the exception of results outside the reference ranges that are deemed not clinically significant by the Investigator (or designee) at Screening and check-in

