^c Clinical Interview for DSM-5 (SCID-5 CT) will be conducted by appropriately trained staff. This psychiatric examination will include an assessment of premorbid personality, personal and developmental history, alcohol and substance use history, forensic history, past psychiatric history. The PRIME questionnaire will also be administered to screen for risk of psychosis. A psychiatric exam (full or partial) can take place at any time during the study at the discretion of the PI, if there is a relevant concern.

^d In all females. Serum pregnancy test at Screening and urine pregnancy tests at all other times. A positive urine pregnancy test will be confirmed with a serum pregnancy test.

^e In all females to determine postmenopausal status.

^f Height measured at Screening only.

^g The genotyping samples will be stored and may be processed and analyzed to assess genotyping of drug metabolizing systems.

^h Day 1 at pre-dose, 1, 4, and 8 hours; day 2 pre-dose; and days 7 and 14 at pre-dose, 1, 4, and 8 hours.

ⁱ For BID Cohorts: Dosing twice daily interval from Day 1 to Day 13, two intakes separated by 12.00 hours (note: only the AM dose is administered on Day 14). For QD Cohorts: Dosing once daily in the morning from Day 1 to Day 14.

^j Timing of PK blood samples may be changed based on emerging data.

^k At each protocol specified timepoint for PK (including predose baseline) out to 12.00 hours postdose. (Section 6.2).

¹ Serial blood will be collected on Day 1, and 14 at predose, 0.5, 1.00, 2.00, 3.00, 4.00, 6.00, 8.00, and 12.00 hours. Trough (predose AM) and 8 hr and 12 hr samples will be collected on Days 2, 7 and 11. Trough samples (predose AM) will be collected on Days 5, 9 and 12. Additional PK samples will be drawn after the last dose on Day 14 at 24.00 (Day 15), 28.00 (Day 15), 48.00 (Day 16), 52.00 (Day 16), 72.00 (Day 17), and 96.00 (Day 18) hours postdose and Day 25 at the follow-up EOS visit (Day25 ± 2 days). Urine will be collected on Day 1 (0 to 4, 4 to 8, 8 to 12, 12 – 24 hr) and Day 14 (0 to 4, 4 to 8, 8 to 12, 12 to 24, 24 to 48 (Day 15), and 48 – 72 hr (Day 16)). See [Table 4](#).

^m Day 1 predose, then 24.00 (Day 2) and 72.00 hours (Day 4) postdose, then every 2 days (Days 6, 8, 10, 12, 14, 16) post dose at approximately 10 am ± 1 hour.

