8.3 Vital Signs

Vital signs will include systolic and diastolic blood pressures, pulse rate, and oral body temperature.

Scheduled time points will include Days 1 and 7: Prior to morning dosing and 0.5, 1.00, 2.00, 3.00, 4.00, 6.00, 8.00, and 12.00 hours. Days 2, 4, 6, 8, 10, and 12: Prior to dosing and 4.00 and 12.00 hours postdose. Day 14: Prior to dosing and 0.5, 1.00, 2.00, 3.00, 4.00, 6.00, 8.00, 12.00, 24.00 (Day 15), 48.00 (Day 16), 72.00 (Day 17), 96.00 (Day 18) hours postdose.

At baseline on Day 1, predose vital sign measurements (except oral body temperature) will be conducted in triplicate (with an interval of approximately 10 - 30 minutes between each recording). The average value of each parameter will be considered as baseline value.

Vital signs will be summarized using descriptive statistics (n, mean, SD, minimum, median, and maximum). All vital signs, including oral temperature, will be listed. Clinically significant abnormal findings will be listed.

Summary tables on observed and change from baseline values will be presented by visit, time point, cohort and pooled placebo and overall.

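### The laboratory summary tables in SAP 8.2 cannot separate treatment-emergent shifts from abnormalities already present at entry, because no change-from-baseline or shift table is planned

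*SAP*

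**What the plan says.** Protocol Section 2 and SAP Table 1 list clinical laboratory tests among the components of the primary endpoint.

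For the summaries, SAP 8.2 says "Laboratory data will be summarized by the type of laboratory test, visit". The content is the usual descriptive statistics of the results, and "the number of subjects with laboratory test results below, within, and above normal ranges will be tabulated by laboratory test and visit". No change from baseline, shift table, cohort or pooled placebo is mentioned. SAP 8.2 also provides listings: "All laboratory data will be listed by laboratory panel and test. Laboratory abnormalities and clinically significant abnormalities will also be listed".

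Protocol 4.1, criterion 13, requires results within the reference ranges, "with the exception of results outside the reference ranges that are deemed not clinically significant" by the investigator at Screening and check-in. An abnormal baseline is therefore allowed.

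A baseline is available. SAP 5.3 defines it as the last non-missing value before first dose, and footnote m to the schedule of activities (Protocol Section 6, Table 3) places laboratory samples at "Day 1 predose, then 24.00 (Day 2) and 72.00 hours (Day 4) postdose", and every two days after that.

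Other components of the primary endpoint are handled differently. For vital signs, SAP 8.3 states "Summary tables on observed and change from baseline values will be presented by visit, time point", split by cohort, pooled placebo and overall. SAP 8.4 plans absolute and change-from-baseline values for ECG intervals. SAP 9.1 to 9.4 define change from baseline for BPRS, CADSS and 3MS. SAP 12 lists only added analysis populations as changes, so it gives no reason for treating laboratory data differently.

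**The concern.** A count of subjects above the normal range at a visit answers a different question from how many subjects moved above it on treatment. The two agree only when nobody was out of range at baseline, and criterion 13 does not ensure that. A subject who enters with a harmless high value adds to every later count in the same way as a subject whose value rose on drug.

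The observed-value statistics have a related limit. They describe the spread between subjects at each visit and say nothing about the spread of change within subjects. A modest, consistent movement in ALT, creatinine or a blood count across six active subjects could stay inside the reference range, be an adverse event in nobody, and be hard to see against between-subject differences. The protocol itself treats laboratory change relative to baseline as informative: one creatinine criterion in 4.3.2.1.1 is a multiple of baseline, and 7.1 allows a shift within the normal range to be an AE. No planned laboratory table displays change of that kind.

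**Working it through.** The plan states no figure on this point, and no formal sample size calculation was done, so there is nothing to reproduce. The check has three parts.

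**1. What marginal counts can identify**

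Take *n* subjects, *b* high at baseline and *v* high at a visit, and let *s* be the number who moved from not-high to high. The subjects high on both occasions number *v − s*, which must lie between 0 and *b*, and *s* cannot exceed *n − b*. Hence

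max(0, *v − b*) ≤ *s* ≤ min(*v*, *n − b*).

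With *n* = 6 active subjects (6:2 allocation, SAP 3.1):

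| High at baseline | High at visit | New shifts |
|---|---|---|
| 0 | 2 | 2 |
| 1 | 1 | 0 to 1 |
| 1 | 2 | 1 to 2 |
| 2 | 2 | 0 to 2 |
| 2 | 3 | 1 to 3 |

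Only the first row, with no abnormal baseline, gives a single answer. A shift table gives a single answer in every row. These figures take the tables as split by dose group; if they are not, active and placebo subjects are mixed as well.

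**2. How often the ambiguity arises**

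The documents give no rate of out-of-range baselines. Assume a rate *p* per test and independent subjects. The chance of at least one among 6 is 1 − (1 − *p*)^6:

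- *p* = 2.5%: 14%
- *p* = 5%: 27%
- *p* = 10%: 47%

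These are for one test. The expected number per test among 6 subjects at *p* = 5% is 6 × 0.05 = 0.3. Protocol Appendix 6 lists 20 numeric chemistry and 11 numeric haematology analytes, 31 in all, so over the whole panel the expectation is 31 × 0.3 = 9.3 out-of-range results per visit in six subjects with no drug effect. The figure of 0.3 is the one that applies to any single table.

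**3. Whether change from baseline would be more precise**

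With equal variances at baseline and post-dose and correlation *r*, Var(change)/Var(raw) = 2(1 − *r*). Change is less variable only if *r* > 0.5. The documents give no *r*. At an assumed 0.7 to 0.9 the ratio is 0.6 to 0.2.

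- Two cohorts (Cohorts 3 and 4 are optional), 6 active v 4 pooled placebo: √(1/6 + 1/4) = 0.65 SD raw. Multiplying by √0.6 and √0.2 gives 0.50 to 0.29 SD.
- Four cohorts, 6 v 8: √(1/6 + 1/8) = 0.54 SD raw, against 0.42 to 0.24 SD.

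Below *r* = 0.5 the direction reverses. SAP 8.2 plans no formal between-group laboratory comparison, so these standard errors only illustrate how sharply a reader could compare groups.

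**The case against.** The strongest reply is that the information is not lost. All laboratory data are listed, abnormalities and clinically significant abnormalities are listed again, and with eight subjects per cohort a reader can follow each one from Day 1 predose. With complete data, the mean change can also be had by subtracting one visit mean from another. Under Protocol 6.1.7, clinically significant post-dose values are reported as AEs as judged by the investigator. SAP 8.1 then separates treatment-emergent from pre-existing events, counts worsening, and tabulates by cohort and pooled placebo. All of this stands. A reader might infer that a treatment-emergent laboratory effect could not be recognised from the trial's output at all; the listings and TEAE tables show otherwise.

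A reader might also infer that dose decisions are compromised. The documents do not support that. The creatinine criterion is applied to individuals during dosing, and the escalation rules in Protocol 4.3.2.2 use subject-level events, not the end-of-study tables.

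What the reply leaves open is aggregate reporting. Tracing by hand is not a planned summary, subtracted means lack the spread of change, and AE capture depends on judging one subject at a time, so a consistent sub-clinical drift can pass through it.

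Table layouts are in a separate document (SAP 13) that is not available here and may include more. SAP 8.2 still does not commit to it, and SAP 5 classes analyses performed after database lock and unblinding as post hoc.

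**Conclusion.** The point holds for the planned summary tables. Once any baseline is out of range, the SAP 8.2 counts leave the number of new shifts as a range: 0 to 2 in the example of 2 of 6 high at both times. No planned laboratory table shows within-subject change. That the counts do not identify the shifts is a matter of arithmetic and needs no assumption; how often it occurs rests on the assumed 2.5% to 10% rate of abnormal baselines.

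The consequence is limited. This is a weakness in how one component of the primary endpoint is summarised, partly covered by the listings and the TEAE tables. It is not a failure of data capture or safety monitoring. A reader might also infer a fixed gain in precision from change scores. The documents give no correlation, and the number of cohorts is not settled, so the reduction from 0.65 SD to 0.50 to 0.29 SD (two cohorts, assumed *r* of 0.7 to 0.9) is an illustration only.

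**What to change.** Amend SAP 8.2 before database lock and unblinding:

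- For each numeric test, present observed value and change from baseline (baseline as in SAP 5.3) by visit, for each cohort, pooled placebo and overall.
- Add low/normal/high shift tables from baseline to the lowest and to the highest post-dose value, with the same grouping. Both extremes are needed because many tests matter in both directions.
- State that unscheduled post-dose results count towards these extremes. This is an exception to SAP 5.1, which keeps unscheduled assessments out of descriptive summaries except for baseline; without it a peak found on a repeat sample could be missed.
- Use the change-from-baseline table to show worsening in subjects already out of range at baseline. A shift table records such a subject as high to high, whereas SAP 8.1 counts worsening as emergent for AEs.

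The cost is one SAP paragraph and two or three standard table shells. No new samples, data or procedures are needed.

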8.2.1 Viral Screen

A screening viral screen will be done for HIV Ag/Ab Combo, Hepatitis B surface antigen, and Hepatitis C virus. The results of the viral screen will be listed.

